11.1.2 Disease Parameters

Measurable disease. Measurable lesions are defined as those that can be accurately measured in at least two dimensions as ≥ 1 cm with spiral CT scan. All tumor measurements should be recorded in centimeters. For CLL, patients without measurable lymph node disease will have measureable disease include lymphocytosis $\geq 5,000/\mu L$ and/or bone marrow involvement.

Non-measurable disease. All other lesions (or sites of disease) including small lesions, (<1 cm using spiral CT scan) are considered non-measurable disease. Bone lesions, ascites, pleural/pericardial effusions, lymphangitis, and cystic lesions are all non-measurable.

Target lesions. All measurable lesions up to a maximum of 6 lesions total, representative of all involved organs, should be identified as **target lesions** and recorded and measured at baseline. Target lesions should be selected on the basis of their size (lesions with the longest SPD

Version Date: 10.23.2019

diameter), and their suitability for accurate repeated measurements (either by imaging techniques or clinically). A baseline sum of the diameters (longest for non-nodal lesions, short axis for nodal lesions) for all target lesions will be calculated and reported as the baseline sum diameters. The baseline sum of the diameters will be used as reference to further characterize any objective tumor regression in the measurable dimension of the disease.

Non-target lesions. All other lesions (or sites of disease) including any measurable lesions over and above the 6 target lesions should be identified as **non-target lesions** and should also be recorded at baseline. Measurements of these lesions are not required, but the presence, absence, or in rare cases unequivocal progression of each should be noted throughout follow-up.

11.1.3 Methods for Evaluation of Disease

All measurements should be taken and recorded in metric notation using a ruler, calipers, or a digital measurement tool. All baseline evaluations should be performed as closely as possible to the beginning of treatment and never more than 4 weeks before the beginning of the treatment.

The same method of assessment and the same technique should be used to characterize each identified and reported lesion at baseline and during follow-up. Imaging-based evaluation is preferred to evaluation by clinical examination unless the lesion(s) being followed cannot be imaged but are assessable by clinical exam.

Conventional CT and MRI. This guideline has defined measurability of lesions on CT scan based on the assumption that CT thickness is 0.5cm or less. If CT scans have slice thickness greater than 0.5 cm, the minimum size of a measurable lesion should be twice the slice thickness.

11.2 Response Criteria

See Appendix A for SLL and MCL. See Appendix B for CLL.

11.2.1 Radiographic Response Review

Radiology will be centrally reviewed by the DF/HCC Tumor Imaging Metrics Core (TIMC).

Each participating site will be responsible for assuring review and confirmation of response as per standard review guidelines at that center. Patients who achieve an objective response may have scans collected and reviewed by independent radiology set up by the Sponsor.

11.2.2 Nodal Partial Response (nPR)

It is anticipated that many patients on this study, particularly in the CLL arm, will experience increased lymphocytosis after starting on the study drugs. This is a well-known phenomenon that is a class effect of the BCR inhibitor drugs. In clinical experience, these patients appear to derive a similar clinical benefit from BCR inhibitors as patients who achieve a traditional PR. Therefore, a revision to the IWCLL criteria was proposed and is now widely recognized. As per Cheson et al., 2012, patients who achieve a radiographic PR but continue to have a

lymphocytosis with >5,000 B-lymphocytes per μ L where the absolute lymphocyte count has not decreased by 50% or more compared to baseline are considered to have a nodal partial response, also known as PR with lymphocytosis.

11.2.3 Evaluation of Best Overall Response

The best overall response is the best response recorded from the start of the treatment until disease progression/recurrence (taking as reference for progressive disease the smallest measurements recorded since the treatment started). The patient's best response assignment will depend on the achievement of both measurement and confirmation criteria as per the MCL and CLL established criteria used in this study (See Appendix A and B).

11.2.4 Duration of Response

Duration of response is defined as the time from documentation of a response to treatment to the first documentation of documentation of tumor progression or death due to any cause whichever comes first. Duration of the response will be summarized using n (sample size), mean, standard deviation, median, minimum, and maximum for the responders.

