5.1.2 Subsequent Cycles

Patients can receive treatment if they do not meet dose delay/dose modification criteria (see section 6). All toxicities must have resolved to grade 1 or less, or the patient's baseline, prior to initiating subsequent cycles.

5.2 Treatment Regimen Phase 1

Cycle = 28 days

|--|

Phase I/Ib Study of TGR-1202 plus Ibrutinib in Patients with Select B-Cell Malignancies

Version Date: 10.23.2019

			CLL		
1 400 mg		560 mg	420 mg		
2 600 mg		560 mg	420 mg		
3 800 mg		560 mg	420 mg		
If ≥ 2 DLT's in either Cohort 1, 3- 6 pts will enroll in Cohort -1 as follows:					
-1	200 mg	560 mg	420 mg		
If ≥ 2 DLT's in a Cohort -1 treatment group, study will be terminated					

Dose level 1 will be the starting level for patients in both the CLL and MCL arms. Patients will continue daily administration of TGR-1202 + ibrutinib until progression or removal from study per investigator decision.

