5.8.1 Pregnancy

During the course of the trial, all female patients of childbearing potential (the definitions of "women of childbearing potential" are listed in Appendix C) must contact the treating investigator immediately if they suspect that they may be pregnant (a missed or late menstrual period should be reported to the treating investigator).

If an investigator suspects that a patient may be pregnant prior to administration of trial drug(s), the trial drug(s) must be withheld until the result of the pregnancy test is confirmed. If a pregnancy is confirmed, the patient must not receive any trial drug(s), and must be discontinued from the trial.

If an investigator suspects that a patient may be pregnant after the patient has been receiving trial drug(s), the trial drug(s) must immediately be withheld until the result of the pregnancy test is confirmed. If a pregnancy is confirmed, the trial drug(s) must be immediately and permanently stopped, the patient must be discontinued from the trial, and the investigator must notify the Overall PI as soon as possible. If a patient becomes pregnant while enrolled in the trial, an SAE

form should be completed and faxed to the Overall PI expeditiously. For more details regarding handling and reporting of pregnancies that occur during treatment, see Appendix C.

5.9 **Duration of Follow Up**

Participants will be followed for survival after discontinuing protocol therapy every 3 months for up to 2 years or until the patient receives their next CLL/MCL-directed therapy or until death, whichever occurs first. Participants removed from protocol therapy for unacceptable adverse event(s) will be followed until resolution or stabilization of the adverse event.

For patients continuing to follow up at the treating institution, regular visits should occur every 3 months and efficacy assessments should occur at the investigator's discretion. For patients no longer treated at the original institution, phone contact should occur every 3 months with documentation of disease status or date of death obtained whenever possible. Patients should be followed for survival every three months for up to two years or until death, or next CLL/MCL directed therapy.

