11.2.5 Progression-Free Survival

Progression-Free Survival: Progression-Free Survival (PFS) is defined as the time from registration to the earlier of progression or death due to any cause. Participants alive without disease progression are censored at date of last disease evaluation.

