13.4 Analysis Plan for Secondary Objectives

Phase I/Ib Study of TGR-1202 plus Ibrutinib in Patients with Select B-Cell Malignancies Version Date: 10.23.2019

The secondary objectives include assessment of the overall response rate, nodal partial response rate, progression-free survival, and duration of response. Due to the exploratory nature, the analysis for secondary endpoints will largely be descriptive. Response rate and duration of response will be summarized descriptively and the Kaplan Meier method will be used to estimate the median progression-free survival time and progression-free survival. A similar descriptive analysis will be performed for laboratory correlative studies of BH3 profiling and pharmacodynamic markers such as phosphorylated levels of AKT, BTK, and ERK, as well as Ki-67 level. If feasible, association between clinical response and laboratory endpoints will be explored.

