14. PUBLICATION PLAN

The results should be made public within 24 months of reaching the end of the study. The end of the study is the time point at which the last data items are to be reported, or after the outcome data are sufficiently mature for analysis, as defined in the section on Sample Size, Accrual Rate and Study Duration. If a report is planned to be published in a peer-reviewed journal, then that initial release may be an abstract that meets the requirements of the International Committee of Medical Journal Editors. A full report of the outcomes should be made public no later than three (3) years after the end of the study.

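### Duration of response is a time-to-event endpoint, but Section 11.2.4 summarises it with a raw mean, SD and median and gives no rule for responses still ongoing at analysis

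*Combined protocol and SAP*

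**What the plan says.** Section 1.3 lists DOR among the secondary objectives. Section 11.2.4 defines it as the time from documented response to the first documented progression or death from any cause, and then fixes the summary: "Duration of the response will be summarized using n (sample size), mean, standard deviation, median, minimum, and maximum for the responders". It does not mention a responder who is alive and progression-free at analysis.

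Section 13.4 treats the two durability endpoints differently in one sentence: "Response rate and duration of response will be summarized descriptively and the Kaplan Meier method will be used to estimate the median progression-free survival time". Section 11.2.5 gives PFS, and only PFS, a censoring rule: "Participants alive without disease progression are censored at date of last disease evaluation".

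Two other provisions determine whether a response will have an observed end. Under Section 5.2 patients "continue daily administration of TGR-1202 + ibrutinib until progression or removal from study per investigator decision". Under Section 5.9, follow-up after treatment takes place "every 3 months for up to 2 years or until the patient receives their next CLL/MCL-directed therapy or until death, whichever occurs first".

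**The concern.** A responder who has not progressed or died has a duration known only to exceed the time observed. A mean, SD or sample median has no place for such a value. The text is silent on what to do, which leaves two options: enter the time observed so far as though the response had ended, or leave the patient out. The two give different answers from the same data, and both tend to be too low.

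Unended responses are to be expected. Patients stay on treatment while they respond. A responder who stops for toxicity and starts another therapy leaves scheduled follow-up at that point, possibly without documented progression.

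The rationale in Section 2.7 is that blocking two points of the pathway may deepen and prolong responses. The stated summary understates durability most where responses last longest. It would also yield a DOR that cannot be set beside the trial's own Kaplan-Meier PFS.

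**Working it through.** The plan attaches no precision or sample-size figure to DOR, so there is none to reproduce. The calculation below shows how large the bias could be.

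**Inputs from the protocol**
- CLL, single-agent ibrutinib: 75% progression-free at 26 months (Section 2.1).
- MCL, single-agent ibrutinib: median PFS 13.9 months (Section 2.1).
- Accrual: about 18 months (synopsis, Study Duration).

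**Assumptions**
- DOR is exponential, and the PFS figures stand in for DOR.
- Entry is uniform over 18 months, and response is documented at month 2.
- Analysis takes place f = 12, 24 or 36 months after last entry. No cutoff is stated: Section 14 refers maturity to a section on sample size, accrual rate and study duration that the protocol does not contain.

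**Hazards**
- CLL: λ = ln(1/0.75)/26 = 0.01106 per month; true median ln 2/λ = 62.6, true mean 1/λ = 90.4 months.
- MCL: λ = ln 2/13.9 = 0.04987 per month; true median 13.9, true mean 20.1 months.

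**Formulas.** Let D be the true duration and C the potential follow-up after response, uniform on (f − 2, f + 16).
- Share ongoing = E[exp(−λC)] = [exp(−λ(f − 2)) − exp(−λ(f + 16))]/(18λ).
- Raw mean, ongoing responses entered as complete = (1 − share ongoing)/λ. Example, CLL at f = 12: (1 − 0.812) × 90.4 = 17.0.
- Raw median solves exp(−λt)·P(C > t) = 0.5. It equals the true median once f − 2 is at least that median.
- Events-only median: the median of D given D ≤ C.

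**Results (months)**

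| | f = 12 | f = 24 | f = 36 | True value |
|---|---|---|---|---|
| CLL: ongoing | 81% | 71% | 62% | – |
| CLL: raw median | 17.1 | 27.8 | 38.3 | 62.6 |
| CLL: raw mean | 17.0 | 26.1 | 34.1 | 90.4 |
| CLL: events-only median | 8.9 | 14.1 | 18.9 | 62.6 |
| MCL: ongoing | 40% | 22% | 12% | – |
| MCL: raw median | 11.8 | 13.9 | 13.9 | 13.9 |
| MCL: raw mean | 12.0 | 15.6 | 17.6 | 20.1 |
| MCL: events-only median | 7.1 | 9.9 | 11.6 | 13.9 |

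Median potential follow-up is f + 7 = 19, 31 and 43 months. The CLL raw median follows that quantity rather than the true 62.6.

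**Sensitivity to the hazard (f = 12/24/36)**
- CLL hazard doubled (true median 31.3, mean 45.2): raw median 15.4/24.5/31.3, raw mean 15.3/22.3/27.6.
- MCL hazard halved (true median 27.8, mean 40.1): raw median 14.9/23.7/27.8, raw mean 14.9/21.4/26.3.
- MCL hazard doubled (true median 7.0, mean 10.0): raw median correct, raw mean 8.3/9.5/9.9.

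**Kaplan-Meier on the same data.** In a very large simulated sample it returns 13.9 for MCL at every cutoff. For CLL the median is not reached, and the 12-month rate is 0.88, matching exp(−0.01106 × 12) = 0.876.

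**The case against.** DOR is one of several secondary endpoints in an analysis that Section 13.4 calls exploratory and largely descriptive. No test, dose decision or sample size uses it, and durability is also covered by PFS, which is properly analysed. This stands, and it limits the severity. It does not rescue the method: Kaplan-Meier is also descriptive, and the same section uses it for PFS.

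A charitable reader might take the listed median as a Kaplan-Meier median, or carry the PFS censoring rule across. Neither fits. The median is listed with a mean, SD, minimum and maximum, and Section 13.4 separates the two endpoints.

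The illustration rests on a PFS proxy from single-agent studies, whereas Phase I admits patients with prior BTK or PI3K inhibitors. The cutoffs are also assumed, and longer follow-up narrows the gap: by the same formulas the CLL raw median is 48.6 at 48 months and 58.8 at 60, against 62.6. The raw mean stays low even then, 47.2 against 90.4 at 60 months. If durations are much shorter than assumed, as in the doubled-hazard MCL case, the bias is small.

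Starting new therapy does not by itself take a patient off study under Section 5.10, so a later progression might still be captured. That is fair. Scheduled follow-up ends there, however, and the number affected is not modelled above.

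Finally, Kaplan-Meier is imprecise at this size. About 18 evaluable patients and a 68% response rate give 18 × 0.68 ≈ 12 MCL responders. With 12, the typical Kaplan-Meier median is about 12.4 months, with a 5th to 95th percentile range of about 6 to 23 at 24 months; the raw median's range is about 7 to 23. For a mature MCL median the change makes little difference. With 13 CLL responders (18 × 0.71 ≈ 13) the Kaplan-Meier median is not reached in about 71% to 92% of simulated trials. That is an honest report of such data; a raw median of 17 months is not.

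**Conclusion.** The point holds and should be fixed. The text alone establishes it: a time-to-event endpoint has been given an uncensored summary, with no rule for unended responses. Leaving them out biases mean and median downward. Entering them at their follow-up time biases the mean downward whenever any are ongoing, and the median only while follow-up is short relative to it.

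The size depends on the assumptions listed (exponential durations, PFS as proxy, assumed cutoffs). On the protocol's own benchmarks, the CLL raw mean at 12 to 36 months is 19% to 38% of the true mean (17.0/90.4 and 34.1/90.4). For MCL it is 60% to 88% (12.0/20.1 and 17.6/20.1), with a sound raw median from 24 months. The effect is confined to the DOR report.

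**What to change.** In Section 11.2.4, replace the summary sentence with a Kaplan-Meier estimate among responders, for each disease group. Responders alive without progression should be censored at their last disease evaluation, as PFS already is. State that this also covers responders who leave follow-up on starting another therapy before documented progression. Report the median with a 95% confidence interval, or as not reached, together with landmark rates and the number still in response. Remove the mean and SD. In Section 13.4, name Kaplan-Meier for DOR as well as PFS.

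The cost is a few sentences of analysis wording. It needs no new data, visits or patients.

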11.2.5 Progression-Free Survival

Progression-Free Survival: Progression-Free Survival (PFS) is defined as the time from registration to the earlier of progression or death due to any cause. Participants alive without disease progression are censored at date of last disease evaluation.

12. DATA REPORTING / REGULATORY REQUIREMENTS

Adverse event lists, guidelines, and instructions for AE reporting can be found in Section 7.0

12.1 **Data Reporting**

12.1.1 Method

The Office of Data Quality (ODQ) will collect, manage, and perform quality checks on the data for this study.

12.1.2 Responsibility for Data Submission

Investigative sites within DF/HCC or DF/PCC are responsible for submitting data and/or data forms to the QACT according to the schedule set by the QACT. Data should be entered within 14 business days of the corresponding visit and within 14 business days of the end of a cycle for any forms to be completed per cycle.

12.2 **Data Safety Monitoring**

The DF/HCC Data and Safety Monitoring Committee (DSMC) will review and monitor toxicity and accrual data from this study. The committee is composed of clinical specialists with experience in oncology and who have no direct relationship with the study. Information that raises any questions about participant safety will be addressed with the Overall PI and study team.

The DSMC will review each protocol up to four times a year or more often if required to review toxicity and accrual data. Information to be provided to the committee may include: up-to-date participant accrual; current dose level information; DLT information; all grade 2 or higher unexpected adverse events that have been reported; summary of all deaths occurring with 30 days of intervention for Phase I or II protocols; for gene therapy protocols, summary of all deaths while being treated and during active follow-up; any response information; audit results, and a summary provided by the study team. Other information (e.g. scans, laboratory values) will be provided upon request.

12.3 Multicenter Guidelines

This protocol will adhere to the policies and requirements of the DF/HCC Multi-Center Data and Safety Monitoring Plan. The specific responsibilities of the Overall PI, Coordinating Center, and Participating Institutions and the procedures for auditing.

- The Overall PI/Coordinating Center is responsible for distributing all IND Action Letters or Safety Reports to all participating institutions for submission to their individual IRBs for action as required.
- Mechanisms will be in place to ensure quality assurance, protocol compliance, and adverse event reporting at each site.
- Except in very unusual circumstances, each participating institution will order the study agent(s) directly from supplier. A participating site may order the agent(s) only after the initial IRB approval for the site has been forwarded to the Coordinating Center.

13. STATISTICAL CONSIDERATIONS

This is a multi-center Phase I/Ib study evaluating the safety of the novel PI3k delta inhibitor TGR-1202 in combination with ibrutinib in patients with relapsed or refractory CLL or MCL. The primary endpoint of this study is to determine the maximum tolerated dose (MTD) in each disease group separately.

13.1 **Determining MTD**

This is a 3+3 design with four doses of TGR-1202 to be considered to determine MTD: 200mg (dose level -1), 400 mg (dose level 1, starting dose), 600 mg (dose level 2), and 800 mg (dose

level 3). Dose limiting toxicities (DLTs) were defined in section 5.6.3.

A cohort of 3 patients will enter at each dose level. If no DLT is seen in the first 3 eligible patients at dose level 1 or 2, a dose escalation will take place. If no DLT is seen in the first 3 eligible patients at dose level 3 or -1, 3 additional patients will be treated at that dose level. If 2 or more of the 3 eligible patients experience a DLT at dose level 1, 2, or 3, the next cohort of 3 patients will be treated at the next lower dose level, unless 6 patients have already been treated at that dose level. If 2 or more of the first 3 eligible patients experience a DLT at dose level -1, the study will be terminated early. If 1 of the first 3 patients experiences a DLT then 3 additional patients will be treated at that dose level. If there is no DLT in the 3 additional patients then dose escalation will take place. If this is dose level 3 or -1, then this dose is the MTD. If 1 or more of the 3 additional patients experience(s) DLT then the MTD is considered exceeded, and 3 more patients are treated at the next lower dose, unless 6 patients have already been treated at that dose level. If this is dose level -1, the study will be terminated early.

A minimum of six patients must be evaluated at the highest tolerated dose level, and fewer than 2 patients in 6 should experience DLT.

Table 5 shows the probability of escalation under various true DLT rates. With this design, there is 91% probability of dose escalation if the true rate of DLT is 10% and 17% probability of escalation if the true DLT rate is 50%.

Table 5: probability of dose escalation

True Rate of DLT	Prob. of Escalation
10%	0.91
20%	0.71
30%	0.49
40%	0.31
50%	0.17
60%	0.08

13.2 Phase Ib

Once the MTD is established, an additional 12 eligible patients in each disease group will be treated at the MTD level to further evaluate the safety of TGR-1202 in combination of ibrutinib. The estimation of toxicity rate will be based on these 12 additional patients. With 12 patients, the 90% confidence interval of the toxicity rate will be within $\pm 25\%$.

